5. OVERALL STUDY DESIGN

[figure not shown]
This is a multi-center, open-label, in-use study.

Subjects will report to the site at Baseline (day 0) visit, will be given an informed consent form, HIPAA form, photography release form, and medical history form to complete.

Subjects will be screened on the basis of the selection criteria for study qualification. Eligible subjects will be assessed at Baseline visit and instructed to start applying the skincare products to the assigned side of the body based on the pre-determined randomization.

Subjects to return to the site at Week 2 (± 3 days), Week 4 (± 5 days), and Week 8 (± 5 days) for follow-ups. The study flow chart is illustrated in Figure 1.

Figure 1. Study Flow Chart

Protocol GLI.04.US.SL.035

CONFIDENTIAL

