Exclusion criteria:	
The presence of any of the following exclusion criteria excluded a subject from enrollment in the study:
 
 1. Pregnant, breastfeeding, or planning pregnancy during the course of the study. 2. Subjects with any known allergies or hypersensitivity to any cosmetics, personal care products, and/or fragrances. 3. History of cancer within the past 5 years 4. History or presence of any skin condition/disease, besides plaque psoriasis, that might interfere with the diagnosis or evaluation of study parameters at the discretion of the investigator. 5. Planning on having surgeries and/or invasive medical procedures during the course of the study 6. Treatment with chemotherapy, immunosuppressive agents, prescription corticosteroids for psoriasis, immunomodulatory therapy (e.g., monoclonal antibodies or antiviral treatment for human immunodeficiency virus or hepatitis C) 7. History or presence of any medical condition that, in the opinion of the Investigator, would make the subject unsuitable for inclusion (e.g., a chronic, relapsing, or hereditary disease that may interfere the outcome of the study). 8. Other condition preventing the subject from entering the study in the Investigator's opinion, (e.g., subjects failing baseline assessments, subjects not likely to avoid other treatments in the treated areas, subjects anticipated to be unavailable or incapable of understanding the study assessments or having unrealistic expectations of the treatment result). 9. Study site personnel, close relatives of the study site personnel (e.g., parents, children, siblings, or spouse), or employees and close relatives of employees at the Sponsor company. 10. Participation in any interventional clinical study within 30 days of screening or planning to participate in another interventional clinical research study while enrolled in this trial.

Investigational Products:	Cetaphil® Moisturizing Cream Cetaphil® Gentle Skin Cleanser Cetaphil® Daily Facial Moisturizer SPF 35 (supporting product)
Treatment Area / Treatment Regimen / Mode of Administration	Step 1: clean the skin with the study cleanser once daily. Step 2: with clean dry hands, apply the study moisturizing cream to the lesion areas. The study moisturizing cream will be applied at least twice daily, in tandem with prescription psoriasis treatment, following the provided instructions. Subjects may apply the test product more frequently as needed.

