8.3 Subject Instructions for the Study

Subjects will be provided with the following instruction to follow during the study:

8.3.1. Study Product Usage Instructions:

The study products are used on both face and body:

- *Step 1: Cleanser* – wet skin with lukewarm water, apply the cleanser to wet skin and massage gently. Rinse well and pat dry.
- *Step 2: Moisturizer* – at least twice daily, in the morning and evening, apply the moisturizer liberally to the lesions and all over the body. Reapply the moisturizer as needed throughout the day.
 - If your psoriasis treatment is topical prescription, you can first apply the prescription treatment following its instruction. Wait at least 10 minutes before applying the study moisturizer to the lesions and all over.
- *Step 3: Sunscreen SPF 35* – if you are planning on spending time outdoors, apply the sunscreen to entire face and body before sun exposure once the moisturizers are fully absorbed.

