8.3.3. General Study Instructions

- Avoid extended periods of sun exposure and use of tanning beds and sunless tanning products for the duration of the study. Extra care should be taken to wear protective clothing, sunscreen, and accessories (such as sunglasses, hat, parasol) and avoid sun exposure from 10 AM to 3 PM.
- Do not use any topical skincare products on the assigned test areas including the affected areas (such as body wash, lotion, cream, oil, ointment), other than the provided study products, for the duration of the study.
- If the affected area is on the face, continue use of all regular brands of color cosmetics, makeup remover, and shaving products if used.
- Do not start using any new skincare or body care products other than the provided study products.

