9.1 Visit Examinations

9.1.1. Visit 1 (Screening / Baseline / Day 0)

Screening and Baseline visit can be combined if subject meets eligibility criteria. The following screening assessments will be performed:

- Obtain ICF and HIPAA form prior to conducting any study specific activity.

Note: Prior to beginning of any study related activities, subjects will be informed about the purpose and nature of the study, the expected post-treatment events, and the potential risks involved with the treatments. Once subjects have completed reading, they will be interviewed to ensure their understanding of the aforementioned forms and be given the

opportunity to ask any study related questions. Subjects declining to sign any of the forms will be dismissed from the study.

- Assess eligibility: review inclusion/exclusion criteria. Subjects failing to meet criteria will be dismissed from the study.
- Record the subject's demographic information, medical history, and concomitant medications.
- Female subjects will need to perform UPT to confirm childbearing potential. The test result must be negative for study qualification.

Once the subject is deemed eligible by the Investigator, the following procedures should be completed:

- Randomize the subject based on the predetermined computer-generated randomization.
- Obtain pre-treatment digital photography of psoriasis lesions, as described in Section 10.2.1, if subject consents.
 - For Site 2 only, perform additional photography (macroscopic, capacitance) of the lesions, as described in Section 10.2.2, 10.2.3.
- Perform investigator clinical grading as described in Section 10.1.
- Perform tolerability assessment as described in Section 11.1.
- Perform QoL questionnaire as described in 10.3.1.
- Dispense study products and diary. Instruct subjects on study product application and diary completion. Remind subjects to bring the study products and diary to the next clinic visit.
- Schedule the next follow-up Visit 2 (Week 2 \pm 3 days).

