10.3.2. Self-Assessment Questionnaire

Subjects will be asked about their perception, satisfaction, and preference with each study treatment using a self-assessment questionnaire at Week 2, 4, and 8, as described in Appendix III.

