12.4 Statistical Analysis Plan

Mean of the change from Baseline will be estimated at applicable post-Baseline timepoint. The null hypothesis, that the mean change from Baseline is zero, will be tested using methods described in

Table 5.

The following will be calculated and reported for each parameter at applicable post-Baseline timepoint(s):

$$\text{Percent mean change from baseline} = \frac{(\text{visit mean score} - \text{baseline mean score})}{\text{baseline mean score}} \times 100$$

$$\text{Percent of subjects improved/worsened} = \frac{(\text{number of subjects improved/worsened from baseline})}{\text{total number of subjects}} \times 100$$

Protocol Version 02: 29 January 2024

This document contains confidential, proprietary information.

Protocol GLI.04.US.SL.035

CONFIDENTIAL

Table 5. Statistical Analysis Plan

Evaluation	Change from Baseline	Notes/Interpretation
Clinical Grading 
 BSA TLSS PGA 	One-sample t-test; If normality fails, a Wilcoxon signed-rank test will be used.	A decrease in scores indicates an improvement.
Tolerability Grading 
 Dryness Burning/Stinging Itching 	One-sample t-test; If normality fails, a Wilcoxon signed-rank test will be used.	A decrease in scores or lack of significant increase indicates tolerability/safety of the treatment products.
Macroscopic Imaging 
 Skin smoothness Skin roughness 	One-sample t-test; If normality fails, a Wilcoxon signed-rank test will be used.	A decrease in values indicates an improvement in skin smoothness. An increase in values indicates an improvement in roughness.
Capacitance Imaging 
 Homogeneity 	One-sample t-test; If normality fails, a Wilcoxon signed-rank test will be used.	An increase in values indicates a homogeneous moisture distribution.
QoL Questionnaire	Wilcoxon signed-rank test	A decrease in response values indicates an improvement.
Self-Assessment Questionnaire	N/A	Percentage of favorable and unfavorable responses will be provided for each question.

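### The protocol randomises subjects to a treated side of the body, yet instructs whole-body use and analyses no side, so the allocation feeds no analysis and the plan has no concurrent comparison

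*Combined protocol and SAP*

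**What the plan says.** On allocation, the Synopsis (Clinical Study Design) and section 5 use the same sentence: eligible subjects start "applying the skincare products to the assigned side of the body based on the pre-determined randomization". Section 9.1.1 turns this into a site procedure at Visit 1: "Randomize the subject based on the predetermined computer-generated randomization". Section 8.3.3 also refers to allocated areas: "Do not use any topical skincare products on the assigned test areas including the affected areas". Those test areas are not defined anywhere.

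On application area, section 8.3.1, which is the text given to subjects, says "The study products are used on both face and body" and tells them to "apply the moisturizer liberally to the lesions and all over the body". The regimen row of the Synopsis says "apply the study moisturizing cream to the lesion areas", with no side named.

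On analysis, section 12.4 reads "The null hypothesis, that the mean change from Baseline is zero, will be tested using methods described in" Table 5. Table 5 lists one-sample t-tests or Wilcoxon signed-rank tests of change from baseline. The objectives in section 4.1 and the efficacy hypotheses in section 4.2 also compare with baseline. The only other test, at the end of section 12.4, sets favourable against unfavourable questionnaire responses.

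**The concern.** A site cannot follow both section 5 and section 8.3.1. If some subjects treat one side and others treat everything, the pooled change mixes differently treated skin, and the mix could differ between the two sites.

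The contradiction also reaches the data rules. Section 7.6 lets the investigator decide whether data are excluded for not following study instructions, and section 12.2 defines the per-protocol set by deviations with substantial impact. Whole-body use departs from section 5, and one-sided use departs from section 8.3.1. Neither rule can be applied consistently until the area is settled.

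The larger stake is the conclusion. Every subject must be on prescription psoriasis treatment and may be starting it at entry (sections 6.3 and 6.5.1). Entry also requires TLSS of at least 6, which invites regression to the mean. Section 4.2 nevertheless says that the products will bring about a significant fall in grading scores. A reader who sees randomisation in the design may take that attribution to rest on a randomised comparison. No such comparison is analysed.

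**Working it through.** **1. Is any side-specific quantity defined?** Taking the sections in order:

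- Unit, ratio and alternatives of the randomisation: not stated in sections 5 or 9.1.1. Table 1 has no randomisation row.
- Treatment of the other side: not stated. Section 7.1 lists a single set of products, two study products and a supporting sunscreen, with no comparator.
- BSA (10.1.1) and PGA (10.1.3): whole-subject measures.
- TLSS (10.1.2): graded on the target lesion. The number of lesions and their side are not given.
- Photography and imaging (10.2.1 to 10.2.3): the subject's lesion, with no side.
- DLQI (Appendix II): whole-subject.
- Tests (12.4, Table 5): no between-side contrast.

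The randomisation therefore has no outcome and no test attached to it. Figure 1 is not reproduced in the copy reviewed, but no figure could remove the conflict between the texts of sections 5 and 8.3.1.

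**2. What can the planned test show?** Section 6.1 gives 40 to 50 completers without power, effect size or SD, so there is no figure in the plan to reproduce. For illustration, let the products add nothing, and let prescription therapy plus regression to the mean give a mean improvement of d SDs of change (d is assumed). For the two-sided 5% one-sample t-test of section 12.1:

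P(significant improvement) = P(T > t(0.975, n−1)), where T is noncentral t with n−1 degrees of freedom and noncentrality d√n.

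| d (assumed) | noncentrality, n=40 | probability, n=40 | noncentrality, n=50 | probability, n=50 |
|---|---|---|---|---|
| 0.3 | 1.90 | 46% | 2.12 | 55% |
| 0.5 | 3.16 | 87% | 3.54 | 93% |
| 0.8 | 5.06 | >99% | 5.66 | >99% |

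A significant result is thus quite compatible with no product effect.

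**3. What precision would a side comparison have?** Assume an SD of TLSS change of 3 points (not in the documents) and n = 40.

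- Current test: half-width of the 95% interval = 2.023 × 3/√40 = 0.96 points. It estimates prescription plus products plus time.
- Paired side difference: SD = 3 × √(2(1−ρ)), where ρ is the between-side correlation of change (not in the documents).
  - ρ = 0.7: SD 2.32, half-width 0.74
  - ρ = 0.5: SD 3.00, half-width 0.96
  - ρ = 0.3: SD 3.55, half-width 1.14
  - ρ = 0: SD 4.24, half-width 1.36

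The paired analysis is at least as precise only if ρ is 0.5 or more. The two intervals also concern different quantities. The products' increment may be smaller than the combined change, so equal width does not mean equal power.

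**The case against.** The best defence is that this is, and was always meant to be, an open-label in-use study compared with baseline. The objectives, hypotheses and Table 5 agree on that, section 8.3.1 is the instruction every subject receives, and the side wording may be left over from another protocol. Section 4.1 already describes the products as used in conjunction with prescription treatment.

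Much of this stands. A reader might infer from section 5 that a randomised untreated-side control was planned and then lost. The documents do not support that: they never call the other side untreated or a control, and they name no comparator. Nor is it shown that any two sites would in fact behave differently; this is a risk, not a finding.

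A reader might also take section 10.3.2, which asks about "perception, satisfaction, and preference with each study treatment", as a trace of a two-treatment design. It need not be. Section 7 defines study treatment as the study products, and Appendix III asks about the cleanser, the moisturizer and the regimen separately. The phrase is coherent in a single-arm study.

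The defence does not remove the contradiction. Randomisation is an operative step at Visit 1, not one stray phrase, and section 4.2 goes beyond section 4.1 by attributing the decrease to the products.

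**Conclusion.** The protocol is wrong as written and must be corrected. It contradicts itself on allocation and application area, and the randomisation it prescribes assigns nothing that is analysed. This rests on the text alone and on no numerical assumption.

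The plan as it stands also has no concurrent comparison, so it cannot support the attribution in section 4.2. The 46% to over 99% at n = 40 (55% to over 99% at n = 50) illustrates how readily the test would be significant without any product effect. It depends on assumed improvements of 0.3 to 0.8 SD.

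It would also be tempting to say that a side comparison would give control at no cost in precision or subjects. That does not follow. Precision depends on an unknown correlation, and section 6.3 does not require a qualifying lesion on each side.

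**What to change.** Reconcile sections 1, 5, 8.3.1, 8.3.3, 9.1.1 and 12.4 to one design. Which application area is right is for the sponsor to decide.

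- **If no side allocation is intended**, which fits the objectives, hypotheses and Table 5: delete the references to an assigned side, assigned test areas and randomisation. Describe the study as single-arm and uncontrolled. Restate section 4.2 as change from baseline under prescription treatment plus skincare products. The cost is amendment wording and a weaker claim.
- **If side allocation is intended**: state what each side receives, make section 8.3.1 match, record TLSS by side at each visit, and add the paired side difference in change to section 12.4. This costs more. It needs a qualifying target lesion on each side, hence a new inclusion criterion or the loss of some subjects, and extra grading at every visit. BSA, PGA and DLQI would remain whole-subject measures. Grading would still be open-label, so the side difference would not be free of assessor bias. Under the assumptions above, its half-width would be 0.74 to 1.14 points for correlations from 0.7 down to 0.3, against 0.96 for the current test.

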6. SELECTION AND DISPOSITION OF STUDY POPULATION

6.1 Number of Subjects

An appropriate number of subjects meeting inclusion/exclusion criteria listed below will be enrolled on the study to achieve minimum 40 (maximum 50 subjects) who complete the study as planned.

Each study site is to enroll and complete with 20-25 subjects, with 40-50 subjects expected to complete when combined.

6.2 Study Population Characteristics

Adult subjects having mild-to-severe plaque psoriasis, with active target lesion plaques, and currently on or starting new prescription treatment for plaque psoriasis.

6.3 Inclusion Criteria

The subjects must meet all the following criteria to be eligible for the study:

1. Adult subjects aged 18 years and above
2. Females or males
3. Any Fitzpatrick skin types I-VI, with effort to include $n = 2$ for each category
4. Any races, with effort to include minimum 10% minority ($n = 4$) such as American Indian or Alaska Native, Eastern/Southeastern Asian, South Asians, Black or African American, Native Hawaiian or Other Pacific Islander.
5. Any ethnicities, with effort to include minimum 10% ($n = 4$) of Hispanic, Latino, or Spanish origin
6. Having active target lesion plaques, with minimum area of 2 cm x 2 cm
7. Having mild-to-severe plaque psoriasis with at least 3% Body Surface Area (BSA) and cumulative Target Lesion Severity Score (TLSS) ≥ 6 .
8. Currently on or starting a plaque psoriasis prescription treatment such as biologics, oral or topical therapy for psoriasis, or UV therapy.
9. Subject in general good health
10. Subject willing to stop using current topical skincare products during the duration of the study.
11. Subject willing to replace current skincare products with study products for the duration of the study.
12. For female subjects of childbearing potential, she must not be pregnant, breastfeeding or planning pregnancy during the course of the study. Subjects must be willing to take a urine pregnancy test (UPT) at Baseline visit.
 - Females of non-childbearing potential, e.g., post-menopausal (absence of menstrual bleeding for 1 year without any other medical reason), hysterectomy, or bilateral ovariectomy, are not required to have a UPT.

Protocol Version 02: 29 January 2024

This document contains confidential, proprietary information.

Protocol GLI.04.US.SL.035

CONFIDENTIAL

13. Ability of giving consent for participation in the study
14. Willing to sign a photography release, with minimum 80% of total study panel
15. Agreement to adhere to the procedures and requirements of the study and to report to the site on the day(s) and at the time(s) scheduled for the assessments.

6.4 Exclusion Criteria

The presence of any of the following exclusion criteria excluded a subject from enrollment in the study:

1. Pregnant, breastfeeding, or planning pregnancy during the course of the study.
2. Subjects with any known allergies or hypersensitivity to any cosmetics, personal care products, and/or fragrances.
3. History of cancer within the past 5 years
4. History or presence of any skin condition/disease, besides plaque psoriasis, that might interfere with the diagnosis or evaluation of study parameters at the discretion of the investigator.
5. Planning on having surgeries and/or invasive medical procedures during the course of the study
6. Treatment with chemotherapy, immunosuppressive agents, prescription corticosteroids for psoriasis, immunomodulatory therapy (e.g., monoclonal antibodies or antiviral treatment for human immunodeficiency virus or hepatitis C)
7. History or presence of any medical condition that, in the opinion of the Investigator, would make the subject unsuitable for inclusion (e.g., a chronic, relapsing, or hereditary disease that may interfere the outcome of the study).
8. Other condition preventing the subject from entering the study in the Investigator's opinion, (e.g., subjects failing baseline assessments, subjects not likely to avoid other treatments in the treated areas, subjects anticipated to be unavailable or incapable of understanding the study assessments or having unrealistic expectations of the treatment result).
9. Study site personnel, close relatives of the study site personnel (e.g., parents, children, siblings, or spouse), or employees and close relatives of employees at the Sponsor company.
10. Participation in any interventional clinical study within 30 days of screening or planning to participate in another interventional clinical research study while enrolled in this trial.

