3. BACKGROUND AND RATIONALE

Psoriasis is a chronic inflammatory skin condition that affects 2% of the population worldwide, and is characterized by the formation of distinct, scaly, erythematous plaques.^{1, 2} These plaques can be painful, pruritic, and disfiguring. Psoriasis can substantially diminish quality of life and negatively affect patient's well-being.² In mild to moderate disease, first-line treatment typically involves topical therapies, such as corticosteroids, vitamin D3 analogues and combination products. Biologic agents have emerged as highly potent treatment options for moderate to severe psoriasis; however, because complete clearance is not always achieved by a biologic agent, most patients who receive biologic therapies continue to use adjunctive topical therapies³.

Skincare products in the treatment of psoriasis have historically been thought to provide only symptomatic relief, but new evidence suggests moisturizers may confer therapeutic benefit by supporting epidermal barrier repair. Patients with psoriasis are advised to moisturize using lipid-replenishing ointments or creams to relieve itching and prevent skin dryness, and as such, frequent application of moisturizers has been standard in the management of psoriasis⁴. Other researchers have noted that moisturizers can confer therapeutic effects in psoriasis⁵. One study involving Cetaphil Moisturizing Cream found that use of moisturizer alone prevented further damage to skin barrier and increased skin hydration⁶. This study is to assess the efficacy of Cetaphil skincare products when used in conjunction with prescription treatment for plaque psoriasis.

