6.5.1. Authorized Therapies

Prescription treatments for plaque psoriasis, including biologics, oral or topical therapy for psoriasis, and UV therapy, are required for this study.

Protocol Version 02: 29 January 2024

This document contains confidential, proprietary information.

Protocol GLI.04.US.SL.035

CONFIDENTIAL

Unless listed under the exclusion criteria (see Section 6.4) or in Prohibited Therapies (see Section 6.5.2), other therapies to treat ongoing conditions are authorized.

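### Exclusion 6 bars immunosuppressive and immunomodulatory treatment with no psoriasis exception, while inclusion 8 and section 6.5.1 admit or require biologic and oral psoriasis drugs

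*Combined protocol and SAP*

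**What the plan says.** Eligibility is conjunctive. Section 6.3 opens with "The subjects must meet all the following criteria to be eligible for the study", and section 6.4 opens with "The presence of any of the following exclusion criteria excluded a subject from enrollment in the study".

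- **Inclusion 8** (section 6.3, repeated in the synopsis) asks for a subject who is "Currently on or starting a plaque psoriasis prescription treatment such as biologics, oral or topical therapy for psoriasis, or UV therapy". It sets no limit by drug class or mechanism.
- **Section 6.5.1** goes further: "Prescription treatments for plaque psoriasis, including biologics, oral or topical therapy for psoriasis, and UV therapy, are required for this study". Its next sentence defers to the exclusion criteria and to section 6.5.2, but the subject of that sentence is a different group: "other therapies to treat ongoing conditions are authorized".
- **Exclusion 6** (section 6.4) bars "Treatment with chemotherapy, immunosuppressive agents, prescription corticosteroids for psoriasis, immunomodulatory therapy (e.g., monoclonal antibodies or antiviral treatment for human immunodeficiency virus or hepatitis C". The synopsis carries the same list, including "immunosuppressive agents, prescription corticosteroids for psoriasis, immunomodulatory therapy". No indication exception, route, dose or time window is given.
- **Section 6.5.2** adds no prohibitions beyond the inclusion and exclusion criteria.
- **Section 3** says that in mild to moderate disease "first-line treatment typically involves topical therapies, such as corticosteroids, vitamin D3 analogues and combination products", and describes patients on biologics as people who mostly keep using topical products alongside them.

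**The concern.** The criterion that brings a subject into the study and one that keeps the subject out can be triggered by the same drug. A site that applies exclusion 6 to the letter turns away subjects whom inclusion 8 and section 6.5.1 admit. A site that treats the psoriasis prescription as exempt enrolls them.

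This matters because of what the study measures. Section 12.4 tests whether mean change from baseline is zero for BSA, TLSS and PGA, with no control comparison planned in its Table 5. The observed change includes whatever the background prescription does, so which prescriptions are allowed in is part of what the result means. Clinical grading combines both sites, while macroscopic and capacitance imaging come from Site 2 alone (section 9, Table 1 footnote). If the sites read exclusion 6 differently, the exploratory imaging could describe a different background-treatment population from the clinical grading.

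**Working it through.** No arithmetic applies to the contradiction itself. The check sets the texts side by side and looks for anything that reconciles them.

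**Step 1: the rule.** By the opening sentences of sections 6.3 and 6.4, a subject is eligible only if every inclusion is met and no exclusion is present. One conflicting pair is enough to make the text impossible to apply to a given subject.

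**Step 2: each treatment class named in inclusion 8, against exclusion 6.**

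| Qualifying treatment | Inclusion 8 and 6.5.1 | Exclusion 6 as written |
|---|---|---|
| Biologic that is immunosuppressive or immunomodulatory | Admitted | Barred |
| Oral drug that is immunosuppressive or immunomodulatory | Admitted | Barred |
| Oral drug that is neither of these, nor chemotherapy or a corticosteroid | Admitted | Not barred |
| Topical corticosteroid | Admitted as topical therapy | Barred, unless the ban is read as systemic only |
| Topical that is neither corticosteroid nor immunosuppressive or immunomodulatory | Admitted | Not barred |
| UV therapy | Admitted | Not barred |

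The first two rows are the contradiction. The documents do not list which drugs count as immunosuppressive or immunomodulatory, so a site has to classify each one.

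**Step 3: is there a precedence rule?** The deference clause in section 6.5.1 covers only therapies other than the psoriasis prescriptions named in the sentence before it. Section 6.5.2 points back to the same criteria, which restates the conflict. Section 6.2 describes subjects on or starting a prescription and adds no limit. The synopsis repeats both criteria unchanged. No precedence rule was found.

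**Step 4: the parenthesis in exclusion 6.** The mention of HIV and hepatitis C may qualify only the antiviral treatment, or the monoclonal antibodies as well. On the first reading, a monoclonal antibody for psoriasis is a named example of what is barred. On the second it is not. Either way the parenthesis only gives examples, and the two class terms keep no indication limit.

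**Step 5: corticosteroids.** Here exclusion 6 does mention psoriasis, but as the target of the ban. Inclusion 8 names topical therapy as a class and does not name corticosteroids, so a deliberate carve-out is possible. It is not stated in inclusion 8 or section 6.5.1. Exclusion 6 gives no route. Nor does it say whether the combination products mentioned in section 3 are covered when they contain a corticosteroid.

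**Step 6: reach.** Section 6.1 plans 20-25 completers per site. With 20 at one site and 25 at the other, one site's reading would apply to between 20/45 = 44% and 25/45 = 56% of completers, and to 50% if the sites are equal. Site 2's reading would apply to all 20-25 imaging subjects. These figures bound whom a site's interpretation could touch. They do not estimate how many subjects take an affected drug. The synopsis lists 2 sites at 3 study centers, so one site may itself cover more than one center.

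**The case against.** The strongest reply is that the intent is reasonably clear. Section 6.5.1 names biologics and oral therapy as required treatments, and section 3 includes biologic users in the rationale, so a sensible investigator would read exclusion 6 as aimed at other diseases. The HIV and hepatitis C wording supports that. This stands as evidence of intent, and it is why the fix below can be specific. It does not make the text consistent: exclusion 6 does not say it, and eligibility should not depend on sites inferring an exception.

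A second reply is that the prescription mix could differ by site even with perfect wording, because inclusion 8 admits any class and no quota or stratification by class is described. That is true. The wording conflict is an avoidable additional source of difference, and divergence between sites is a possibility rather than a demonstrated fact.

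A third reply is that the corticosteroid ban is intended. The documents allow that reading, so a reader who infers that topical corticosteroids are a second outright contradiction goes too far. What is missing is a statement of the carve-out and its route.

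A reader might also infer that nobody can be enrolled. The documents do not support that: UV therapy, and topicals that are neither corticosteroid nor immunosuppressive or immunomodulatory, pass both criteria, as do oral drugs outside the barred classes.

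**Conclusion.** The eligibility text is wrong as written for biologic and oral psoriasis drugs that are immunosuppressive or immunomodulatory: the same drug satisfies a required inclusion and triggers an exclusion, and nothing resolves it. It should be fixed. For corticosteroids the finding is narrower: a possibly deliberate limit that is not carried into inclusion 8 or section 6.5.1.

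The size in subjects cannot be computed, because no treatment mix is given. The conclusion assumes only that at least one biologic or oral drug used to qualify under inclusion 8 would be classed as immunosuppressive or immunomodulatory. Exclusion 6 itself gives monoclonal antibodies as an example of the latter, subject to the ambiguity in its parenthesis.

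A reader might go on to infer a loss of sample size or precision, through subjects on a barred drug being kept for safety evaluation only under section 6.5.2. The documents do not support a figure. The affected share is unknown. If exclusion 6 is enforced at screening, such subjects never enter. Section 12.2 keeps treated subjects with a follow-up visit in the primary efficacy set, and section 9.2 uses data collected up to withdrawal. How data after a prohibited therapy are handled is a separate question. This finding changes no test, endpoint or hypothesis.

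**What to change.** In exclusion 6, in both section 6.4 and the synopsis, limit chemotherapy, immunosuppressive agents and immunomodulatory therapy to treatment *for conditions other than plaque psoriasis*, and add: *Biologics and non-corticosteroid oral therapy prescribed for plaque psoriasis are allowed.*

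The sponsor's clinical team then decides on corticosteroids:

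- **If the ban is kept**, state its route (topical, oral or both) and whether combination products containing a corticosteroid are covered. Write the same limit into inclusion 8 (section 6.3 and synopsis) and section 6.5.1. If the ban is topical only, bring the word *non-corticosteroid* in the added sentence into line with it.
- **If the ban is not intended**, delete it and drop *non-corticosteroid* from the added sentence.

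The word *non-corticosteroid* matters while the ban has no route: a sentence allowing all oral therapy would conflict with it inside the same criterion.

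The cost is wording in 2 places if the ban is deleted (exclusion 6 twice) or 2 + 3 = 5 places if it is kept (plus inclusion 8 twice and section 6.5.1). Section 14.6 requires a written amendment and IRB approval. Visits, assessments, sample size and analyses do not change.
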